9.2 Clinical Laboratory Evaluations

The following laboratory tests will be performed:

Hematology	Complete blood count (including hemoglobin, platelet count and white blood cell count) and absolute counts for neutrophils, lymphocytes, eosinophils, and monocytes.
Serum Chemistry	Alanine aminotransferase (ALT), aspartate aminotransferase (AST), alkaline phosphatase, total bilirubin, gamma glutamyl transferase (GGT), creatinine, blood urea nitrogen, lactate dehydrogenase (LDH), glucose, albumin, sodium, potassium, chloride, bicarbonate, and calcium.
Urinalysis	Specific gravity, pH, glucose, protein, blood, ketones, bilirubin, urobilinogen, nitrite, leukocyte esterase by dipstick.
Other tests	HIV, hepatitis B and C, urine drug screen, and serum pregnancy test (females only)

The hematology, serum chemistry, and urinalysis tests will be performed at the timepoints indicated in the schedule of assessments (schedule of assessments can be found in [Section 15](#)).

All laboratory values collected at visits will be included in the summaries and listings.

Descriptive summaries of observed value and change from baseline (last result available on or before Day 1) at each scheduled post baseline visit will be presented by treatment group for each continuous parameter for the safety population, both in tabular format and as boxplots. For participants who have an abnormal on-study laboratory result, longitudinal (spider) plots for hematology, serum chemistry, and urinalysis parameters will be produced.

Tables of the worst shift in FDA Toxicity Grading Scale in laboratory values from Day 1 (baseline) to visit Day 8, visit Day 91, visit Day 151 will be also presented per parameter, for those parameters that have FDA Toxicity Grading Scale grading. Values that aren't within any toxicity criteria will be presented as 'Normal'.

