### 8.1. Safety Assessments

The screening visit will take place between 30 days and 2 days before the planned Day 1 visit.

All participants will also be required to attend the Day -1 (Pre-V1) visit within 24 hours before planned dosing to begin confinement.

A negative serum pregnancy test (based on the serum sample collected on Day -1) must be confirmed prior to study intervention administration on Day 1.

All Day 1 safety assessments and sample collections are prior to administration of study intervention.

Prior to opening Cohorts 2 and 3 together, Cohort 4, and Cohort 5, respectively, to enrollment, the SRT will conduct safety assessment of data for the previous cohort/s collected when all participants in the currently dosed cohort have completed Day 15.

During each IV infusion, any infusion reactions will be recorded.

Planned time points for all safety assessments are provided in the SoA.

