#### **8.1.7. Clinical Safety Laboratory Assessments**

Clinical safety laboratory assessments will be performed at screening, on Day -1 (Pre-V1), and throughout the study at timepoints specified in the SoA (Section 1.3).

Blood samples for laboratory assessments will be collected at screening, and at study visits indicated in the SoA.

Laboratory values from the most recent blood sample collected prior to randomization that are outside the normal range that are suggestive of a disease state (i.e., clinically significant Grade 1 abnormalities or values greater than Grade 1 [refer to Section 10.4]) will lead to exclusion from study enrollment, with the exception of any grade hematuria in a menstruating female, or a urinalysis abnormality judged not clinically significant by the investigator.

Refer to Section 10.4 for toxicity table for grading for each clinical laboratory test.

Clinical safety laboratory parameters that will be evaluated include:

- a. Hematology: Complete blood count (including hemoglobin, platelet count and white blood cell count) and absolute counts for neutrophils, lymphocytes, eosinophils, and monocytes

- b. Serum chemistry: alanine aminotransferase (ALT), aspartate aminotransferase (AST), alkaline phosphatase, total bilirubin, gamma glutamyl transferase (GGT), creatinine, blood urea nitrogen, lactate dehydrogenase (LDH), glucose, albumin, sodium, potassium, chloride, bicarbonate, and calcium.
- c. Urinalysis: Specific gravity, pH, glucose, protein, blood, ketones, bilirubin, urobilinogen, nitrite, leukocyte esterase by dipstick.

Abnormal results and findings that make the participant ineligible for study participation will be discussed with the participant and the participant will be referred for follow-up care with their health care provider if necessary.

All screening laboratory specimens will be processed according to laboratory SOPs available from the clinical laboratory(ies) designated for the study.

All protocol-required safety laboratory tests will be performed by the site local laboratory or at the point of care. Laboratory safety testing performed at point of care will be documented in participant source and captured in the electronic data capture (EDC) database.

Information about the laboratory(ies), including any instructions for performing and interpreting specific tests, will be maintained in the investigator's study files.

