The investigator must review the laboratory report, document the review, and record any clinically relevant changes occurring during the study in the AE section of the CRF. The laboratory reports must be filed with the source documents.

All protocol-required laboratory assessments must be conducted in accordance with the Laboratory Manual and the SoA.

If laboratory values from non-protocol-specified laboratory assessments require a change in participant management or are considered clinically significant by the investigator (e.g., AE or SAE), then the results must be recorded in the CRF.

Additional tests may be performed at any time during the study as determined necessary by the investigator or required by local regulations.

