- RSM01 – 300 mg IV (Cohort 1)
- RSM01 – 300 mg IM (Cohort 2)
- RSM01 – 1000 mg IV (Cohort 3)
- RSM01 – 3000 mg IV (Cohort 4)
- RSM01 – TBD mg IM (Cohort 5)
- Total RSM01 treatment group
- Placebo IV (Cohorts 1, 3, 4)
- Placebo IM (Cohorts 2, 5)
- Total Placebo treatment group

All data listings will be sorted by cohort, treatment group, and participant number.

Study days are calculated with respect to study intervention administration date as below:

- If the assessment/observation date is on or after study intervention administration date, then Study Day = Assessment/Observation Date – Study Intervention Administration Date + 1.
- Otherwise, Study Day = Assessment/Observation Date – Study Intervention Administration Date.

Baseline will be defined as the last non-missing assessment (including repeated and unscheduled assessments) before study intervention administration, unless otherwise specified. If a patient

was rescreened, data from the rescreening period and not the original screening period will be used in the analyses as applicable.

For summary of safety assessments, if there are repeated measurements at a time point, the first non-missing assessment at that time point will be used in the summary tables.

For ADA-positive participants, the date of the first positive ADA result will be considered as the start date of ADA response.

Time to post-baseline ADA detection (weeks) will be calculated as:

$$\begin{aligned} & (\text{Date of first positive ADA assessment} - \text{Study Intervention Administration} \\ & \quad \text{Date} + 1) / 7 \end{aligned}$$

If the first positive ADA is prior to the start of treatment, the formula is revised to:

$$(\text{Date of first positive ADA assessment} - \text{Study Intervention Administration Date}) / 7$$

Duration of ADA immunogenicity response (weeks) is defined as:

$$(\text{Date of last positive ADA assessment} - \text{date of first positive ADA assessment} + 1) / 7$$

For participants with pre-existing positive, duration will be calculated from administration date of RSM01 rather than from date of first positive assessment.

The methodology and data handling specifications for PK data are detailed in [Section 8](#).

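### The laboratory baseline is fixed by date, not by time of dosing, so an unscheduled post-dose draw on Day 1 would become the reference for that participant's later results

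*SAP*

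**What the plan says.** SAP Section 4 gives the general rule: "Baseline will be defined as the last non-missing assessment (including repeated and unscheduled assessments) before study intervention administration, unless otherwise specified". For laboratory data, SAP 9.2 gives a different one. Its summaries show "change from baseline (last result available on or before Day 1) at each scheduled post baseline visit", and protocol 9.3.2 uses the same words. SAP 9.2 then plans "Tables of the worst shift in FDA Toxicity Grading Scale in laboratory values from Day 1 (baseline) to visit Day 8", and likewise to Day 91 and Day 151. Protocol 9.3.2 labels the baseline of its shift summaries in the same way.

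The schedules in both documents place safety laboratory tests at screening and Day -1, then at Day 8, Day 91, Day 151 and the discontinuation visit. None is scheduled on Day 1. Protocol 8.1.7 adds: "Additional tests may be performed at any time during the study as determined necessary by the investigator".

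**The concern.** Safety laboratory parameters are a secondary endpoint. A baseline is useful only if it precedes the exposure whose effect is being described. The laboratory rule goes by calendar date, and the dosing day includes the hours after dosing.

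Participants are on site during those hours: through Day 3 in the Dose Escalation Phase, and for at least 4 hours in Cohort 5. Protocol 10.2.5 obliges the investigator to arrange supplemental evaluations of an adverse event when medically indicated, and these may include laboratory tests. A post-dose sample on Day 1 is therefore foreseeable. If one is taken, the rule as written uses it as the starting point for that participant's later laboratory results. In arms of six, one such participant is visible in the mean.

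**Working it through.** The plan states no figure on this point, so there is none to reproduce. The check is textual, followed by arithmetic on assumed values.

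**Which rule governs.** The Section 4 definition applies only "before study intervention administration, unless otherwise specified". SAP 9.2 specifies something else for laboratory data, so by the SAP's own precedence 9.2 governs.

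**What Day 1 covers.** Section 4 says "Study days are calculated with respect to study intervention administration date as below". The calculation uses dates and no clock times, so every result on the dosing date is a Day 1 result.

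**What can fall on Day 1.** No safety lab is scheduled then, so any Day 1 result is unscheduled. If there is none, both rules normally return the Day -1 value. If there is a pre-dose recheck, both return the recheck. They differ only for a draw after dosing.

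**Size of the error when they differ.** Write B for the last pre-dose value, P for the post-dose Day 1 value and V for the value at a later visit.

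- Change with a pre-dose baseline: V - B
- Change under 9.2 as written: V - P
- Error: (V - P) - (V - B) = B - P

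V cancels, so the same error enters at Day 8, Day 91 and Day 151. One affected participant moves an arm mean by (B - P)/n.

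All laboratory values below are assumed. The grades are those of protocol Table 9; haemoglobin grades use its change-from-baseline rows (fall up to 1.5 g/dL Grade 1, 1.6 to 2.0 Grade 2, 2.1 to 5.0 Grade 3).

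| Case | B (Day -1) | P (Day 1, post-dose) | V (Day 8) | V - B | V - P |
|---|---|---|---|---|---|
| WBC, cells/mm³ | 7,000 | 16,000 | 7,000 | 0 | -9,000 |
| Haemoglobin, woman, g/dL | 14.0 | 13.0 | 12.2 | -1.8 (Grade 2) | -0.8 (Grade 1) |
| Haemoglobin, fall persists | 14.0 | 11.5 | 11.5 | -2.5 (Grade 3) | 0.0 (no change grade) |
| Haemoglobin, partial recovery | 14.0 | 11.5 | 12.5 | -1.5 (Grade 1) | +1.0 (no change grade) |

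Effect on the arm mean:

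- WBC: -9,000/6 = -1,500 cells/mm³ at n=6, and -9,000/24 = -375 at n=24.
- Haemoglobin with B - P = 2.5: 2.5/6 = 0.42 g/dL at n=6, and 2.5/24 = 0.10 at n=24.

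Effect on the shift:

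- The WBC case reads Normal to Normal with a pre-dose baseline. As written it reads Grade 2 to Normal, because 16,000 lies in the 15,001 to 20,000 band.
- In the persisting case, for a woman on the absolute scale (Grade 1 is 11.0 to 12.0), Normal to Grade 1 becomes Grade 1 to Grade 1.

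The second row is specific to women. A value of 12.2 lies outside every female absolute band, so the change row is the only signal. In a man, 12.2 is already Grade 2 on the absolute scale (10.5 to 12.4), whatever the baseline.

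GGT is exposed in a similar way. Its scale in Appendix 4 switches from multiples of the upper limit of normal to multiples of baseline when baseline is abnormal.

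**The case against.** The best defence is that the intent is plainly pre-dose. Protocol 8.1 states "All Day 1 safety assessments and sample collections are prior to administration of study intervention", and footnotes to the SAP schedules say much the same. This supports the intent but does not settle the rule. The same schedules take PK samples after dosing on Day 1, so the statement is not literally about every sample, and it does not bind a test ordered for cause.

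A second defence is that a Day 1 laboratory result may be a legitimate pre-dose recheck. Protocol 8.1.7 judges eligibility on the latest sample before randomization, and randomization is on Day 1. That stands, and the corrected definition keeps such a result.

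A reader might infer that the rule hides the acute event, removes it from the shift table or treats it as pre-existing. The documents do not support this:

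- Change from baseline is shown at scheduled visits, and shifts only at Day 8, 91 and 151. An unscheduled Day 1 value would not appear there as a post-baseline result under either definition.
- Clinically relevant changes go into the AE section of the CRF (protocol 8.1.7), and laboratory parameters of Grade 1 and above go into the AE log (protocol 8.2).
- SAP 9.1.1 defines treatment emergence relative to dosing, not to the laboratory baseline.
- The laboratory pausing rule rests on the investigator's assessment and is not stated to use the SAP baseline.

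It is also true that the study is descriptive and tests no hypothesis on laboratory data.

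**Conclusion.** The definition is wrong as written, with a conditional and limited effect. It overrides the SAP's own pre-dose rule and, read literally, accepts a post-dose value as baseline. The harm is a contaminated reference for later visits: a persisting change is shrunk or erased, and recovery appears as a change in the opposite direction.

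The error for an affected participant is B - P at every later visit. In the assumed WBC case that is -9,000 cells/mm³, or -1,500 on the mean of a six-person arm. This rests on three assumptions: that an unscheduled lab is drawn after dosing on Day 1, that the programmer follows 9.2 rather than Section 4, and, for the haemoglobin and GGT grades, that they are derived from the analysis baseline.

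A reader might suppose that such draws are common. The documents give no frequency, so the expected effect on the study's tables cannot be estimated, and participants without such a draw are unaffected.

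**What to change.** In SAP 9.2, mirrored in protocol 9.3.2, replace the parenthetical with *last non-missing result before the date and time of study intervention administration*. In the shift tables, replace the Day 1 label with *baseline* so defined. If the protocol is not amended for this alone, record the difference in the SAP.

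The cost is one phrase in each document and a table label. No new assessments are needed, only the collection time of any Day 1 laboratory sample. The correction does not require adding unscheduled Day 1 values to a worst post-baseline grade; that would be a separate design choice.

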**Table 7: Summary of Primary and Secondary Endpoints and Analyses**

Endpoint	Statistical Analysis
Primary:	
Unsolicited AEs through Day 151	The incidence and Clopper-Pearson 95% CIs of AEs and SAEs/AESIs will be summarized by treatment group, dose levels, routes of administration and overall, and by intensity.
All SAEs/AESIs through Day 151	Duration, day of onset of local and systemic solicited AEs will be summarized by group. Relationship of unsolicited AEs and SAEs/AESIs to the study intervention will be summarized by group.
Solicited systemic AEs through Day 7	Any infusion reactions will be described.
Solicited local AEs for injection site reactions for 7 days after dose administration (only applies to IM doses)	
Secondary:	
Safety laboratory parameters Grade 1 and above through Day 151	The incidence of safety parameters outside of normal ranges (Grade 1 and above), change from baseline, grades, grade shifts, as applicable, will be summarized by treatment group, dose levels, routes of administration and overall, and by intensity, and relationship to the study intervention.
PK parameters  AUC 0-∞ , CD 91 , AUC 0-D91 , CD 151 , AUC 0-D151 C max , C min , T max , t 1/2 , CL and V Z	RSM01 capillary blood concentrations and PK parameters will be summarized by treatment group using descriptive statistics, and the number of participants. Following summaries will be provided arithmetic mean, standard deviation, arithmetic percent CV, median, minimum, maximum, geometric mean, and geometric percent CV.  The proportion of participants with observed or predicted CD 151 concentrations above the EC 90 will be summarized by treatment group and country, as appropriate.
Incidence of ADAs to RSM01 through Day 151	ADA incidence will be summarized by treatment group. Exact analyses will be pre-specified in the SAP.

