### **9.3.2. Safety Secondary Laboratory Assessments**

Clinical safety laboratory evaluations are listed in Section 8.1.7. All laboratory values collected at visits will be included in the summaries and listings. Descriptive summaries (n, mean, standard deviation, median, minimum, and maximum) of observed value and change from baseline (last result available on or before Day 1) at each scheduled post baseline visit will be presented for each continuous variable test parameter.

Summaries by toxicity grade and grading shifts in laboratory values from Day1 (baseline) to Day 8, Day 91, and Day 151 visits will be also presented.

The frequency of safety laboratory parameters outside the normal range will be summarized by treatment group.

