#### 10.2.5.1. Assessment of Intensity

The investigator will assess the intensity of each AE reported during the study. In the case of local reactions, vital signs, systemic events, and laboratory abnormalities, the Grades delineated in Section 10.4, Appendix 4 will be employed.

In the case of an AE or abnormal clinical laboratory result not included in Appendix 4, intensity will be assigned using the Grades described in the U.S. Department of Health and Human Services, Common Terminology Criteria for Adverse Events, Version 5.0 [US HHS 2017] as follows:

**Grade 1 Mild;** asymptomatic or mild symptoms; clinical or diagnostic observations only; intervention not indicated.

**Grade 2 Moderate;** minimal, local or noninvasive intervention indicated; limiting age-appropriate instrumental Activities of Daily Living (ADL)\*

**Grade 3 Severe** or medically significant but not immediately life-threatening; hospitalization or prolongation of hospitalization indicated; disabling; limiting self-care ADL\*\*symptoms, causing inability to perform usual social and functional activities with intervention or hospitalization indicated

**Grade 4 Life-threatening consequences;** urgent intervention indicated

Notes:

A semi-colon indicates 'or' within the description of the grade.

\*Instrumental ADL refers to preparing meals, shopping for groceries or clothes, using the telephone, managing money, etc.

\*\*Self-care ADL refers to bathing, dressing, and undressing, feeding self, using the toilet, taking medications, and not bedridden.

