2.2 Secondary Objectives and Endpoints

Secondary objectives	Endpoint description

• To characterize safety laboratory parameters following RSM01 administration	
• Safety laboratory parameters through Day 151

• To characterize the pharmacokinetics (PK) following RSM01 administration	
PK parameters including:
 
• Area under the capillary blood-concentration time curve from zero to infinity ($AUC_{0-\infty}$)• Day 91 concentration and area under the capillary blood-concentration time curve (C_{D91} and AUC_{0-D91})• Day 151 concentration and area under the capillary blood-concentration time curve (C_{D151} and AUC_{0-D151})• Maximum capillary blood-concentration (C_{max} following IM administration and C_0 following IV administration)• Minimum concentration (C_{min})• Time to maximum capillary blood-concentration (T_{max}) and apparent terminal half-life ($t_{1/2}$)• Systemic clearance (CL for IV or CL/F for IM)• Volume of distribution of RSM01 (V_z for IV or V_z/F for IM) through Day 151

• To characterize the formation of anti-drug antibodies (ADAs) following RSM01 administration	
• Incidence of ADAs to RSM01 through Day 151

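### SAP 9.2 omits the protocol's table of laboratory values outside the normal range, so 12 of 32 scheduled tests have no abnormal-value count in the laboratory tables it specifies

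*SAP*

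**What the plan says.** Protocol 9.3.2 plans descriptive summaries, then summaries by toxicity grade and grade shift, and then a further item in its own paragraph: "The frequency of safety laboratory parameters outside the normal range will be summarized by treatment group". Protocol Table 7 gives the analysis of this secondary endpoint as "The incidence of safety parameters outside of normal ranges (Grade 1 and above), change from baseline, grades, grade shifts, as applicable".

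SAP 9.2 plans observed values and change from baseline for continuous parameters, as tables and boxplots. It adds spider plots for participants with an abnormal on-study result, and it says all values go into the summaries and listings. Its only specified categorical laboratory output is a set of worst-shift tables, which "will be also presented per parameter, for those parameters that have FDA Toxicity Grading Scale grading". It adds: "Values that aren't within any toxicity criteria will be presented as 'Normal". No out-of-range frequency is named.

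SAP 2.2 words the endpoint as "Safety laboratory parameters through Day 151", without the protocol's restriction to Grade 1 and above.

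For the investigator's grading, Protocol 10.2.5.1 says that for an AE or "abnormal clinical laboratory result not included in Appendix 4, intensity will be assigned using the Grades described in" CTCAE v5.0. Appendix 4 writes out the CTCAE criteria for GGT because the FDA tables do not grade it.

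**The concern.** A programmer who follows SAP 9.2 will not produce an analysis that the protocol assigns to a secondary safety endpoint. The SAP states that it is based on protocol v4.0, and Protocol 10.1.6 says modified analyses belong in the relevant analysis plan, yet the SAP does not mention this one. SAP Section 12 covers only later changes from the SAP itself.

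This is a first-in-human trial with 6 RSM01 recipients in each escalation cohort and 8 placebo recipients in all. In groups of that size, a laboratory signal is likely to be a few participants crossing a limit. A count by treatment group shows that directly, while a mean change may not.

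The FDA-scale shift tables cannot stand in for the missing table. They leave out every test that is not on the scale, and for tests on it they treat any value that meets no criterion as normal.

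**Working it through.** The plan states no figure on this point, so the check is a count of tests and a comparison of texts.

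**Inputs.** The scheduled tests come from SAP 9.2 (the same list as Protocol 8.1.7). The complete blood count is taken as its three named components plus the four absolute counts. The FDA-scale rows come from Protocol Appendix 4, Tables 9 and 10.

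| Panel | Tests listed | With an FDA row | Without an FDA row |
|---|---|---|---|
| Hematology | 7 | 6 | 1: monocytes |
| Serum chemistry | 15 | 11 | 4: GGT, LDH, chloride, bicarbonate |
| Urinalysis | 10 | 3: protein, glucose, blood | 7: specific gravity, pH, ketones, bilirubin, urobilinogen, nitrite, leukocyte esterase |
| Total | 7 + 15 + 10 = 32 | 6 + 11 + 3 = 20 | 1 + 4 + 7 = 12 |

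Share without an FDA row: 12/32 = 37.5%.

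**Sensitivity of the count.**
- If GGT were graded by the protocol's CTCAE criteria despite the SAP's FDA-only wording: 11/32 = 34.4%.
- Table 10 grades urine blood by microscopy, but the scheduled test is a dipstick. If the dipstick result cannot be mapped to that criterion: 13/32 = 40.6%, with 8 of 10 dipstick tests uncovered.
- SAP Section 4 promises frequencies and percentages for categorical variables. Assume it is applied to ketones, bilirubin, urobilinogen, nitrite and leukocyte esterase, and that a category frequency serves as the abnormal count. Then 12 − 5 = 7 tests remain: 7/32 = 21.9%.

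**Graded tests: out of range compared with no criterion met.**
- Table 9 grades platelets, neutrophils, lymphocytes and albumin for decreases only. A value above the upper limit meets no criterion and would be labelled normal.
- ALT, AST and alkaline phosphatase reach Grade 1 at 1.1 × ULN. A value of, say, 1.05 × ULN is outside the range, meets no grade, and would be labelled normal.

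The two measures therefore differ even where a grade exists.

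**What still captures an abnormal result in the 12 tests.** It appears in the listings, the spider plots and, for continuous tests, the descriptive tables and boxplots. If it is reported as a treatment-emergent AE, SAP 9.1.1 tabulates it by system organ class, preferred term, severity and relationship. None of these is the out-of-range frequency by treatment group that Protocol 9.3.2 describes.

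**The case against.** The strongest reply is that little is lost. Protocol 8.2 sends laboratory parameters of Grade 1 and above to the AE log, Protocol 8.1.7 has clinically relevant changes entered in the AE section of the CRF, and results outside Appendix 4 are graded by CTCAE. The SAP then counts treatment-emergent AEs by treatment group. Minimum, maximum, boxplots, spider plots and listings would make a cluster of abnormal values visible. The trial is descriptive, with no hypothesis testing of safety.

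Much of this stands. A reader might infer that abnormal results in these tests are never counted, or that some dipstick tests get no summary at all. The documents support neither: AE-reported abnormalities are tabulated, all values are listed, and SAP Section 4 can be read as giving dipstick frequencies. But the AE route is not equivalent. Protocol 8.2 says only that chemistry and hematology results may qualify as AEs, and Protocol 10.2.1 ties the definition to the investigator's judgment of clinical significance. A count against the laboratory's range does not depend on that judgment.

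A second reply is that Table 7 explains out of range as Grade 1 and above, so the shift tables already show the incidence. Table 7 alone permits that reading. Protocol 9.3.2 does not fit it well, because it lists the out-of-range frequency separately from the grade summaries, and the platelet and ALT examples show that the two differ.

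A reader might also take the wording of SAP 2.2 as a loss. It is the reverse: without the grade restriction the endpoint is broader. Nor does Protocol 10.2.5.1 require CTCAE grades in the shift tables. It governs the investigator's assessment, and GGT is the only scheduled test for which the documents give test-specific CTCAE thresholds.

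**Conclusion.** The point holds as a departure of the SAP from the protocol that should be corrected. SAP 9.2 leaves out a protocol-specified analysis of a secondary safety endpoint without explanation. Twelve of 32 scheduled tests (37.5%; 11 to 13 depending on how GGT and dipstick blood are handled) have no abnormal-value count in any laboratory frequency or shift table it specifies. If SAP Section 4 is read generously for the five categorical dipstick tests, 7 remain. In addition, out-of-range values of graded tests that meet no FDA criterion would be presented as normal.

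This rests on reading Protocol 9.3.2 as asking for more than graded abnormalities, and on taking SAP 9.2 as the full specification of the laboratory tables. No data go uncollected or unlisted. What is missing is a frequency by treatment group that does not depend on AE reporting.

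**What to change.** In SAP 9.2:

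1. Add the protocol's table: number and percent of participants with any post-baseline value below, and any above, the laboratory's normal range, by treatment group, for every scheduled test with a reference range. Show dipstick tests as normal or abnormal.
2. Include GGT in the shift tables, graded by the CTCAE v5.0 criteria in Protocol Appendix 4.
3. Replace the label for values meeting no criterion with wording such as *no toxicity criterion met*.

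If the sponsor prefers not to produce the table, the SAP should record the departure from Protocol 9.3.2 and the reason.

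Leave the wording of SAP 2.2 as it is. Restoring the grade restriction would narrow the endpoint and conflict with counting ungraded tests. Do not require CTCAE grades for tests for which the documents give no thresholds.

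Cost: a short SAP edit and one or two extra tables from data already collected. The spider plots already require abnormal results to be identified. No new samples or visits are needed.
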